APPENDIX IX: CYP3A4 SUBSTRATES, INDUCERS AND INHIBITORS

This is NOT an all-inclusive list. Because the lists of these agents are constantly changing, it is important to regularly consult frequently updated medical references.

CYP3A4 substrates	Strong Inhibitors ¹	Moderate Inhibitors	Strong Inducers	Moderate Inducers
acalabrutinib ⁵ alfentanil ^{4,5} amiodarone ⁴ aprepitant/fosaprepitant atorvastatin axitinib bortezomib bosutinib ⁵ budesonide ⁵ buspirone ⁵ cabozantinib calcium channel blockers cisapride citalopram/escitalopram cobimetinib ⁵ conivaptan ⁵ copanlisib crizotinib cyclosporine ⁴ dabrafenib dapsone darifenacin ⁵ darunavir ⁵ dasatinib ⁵ dexamethasone ² diazepam dihydroergotamine docetaxel doxorubicin dronedarone ⁵ eletriptan ⁵ eplerenone ⁵ ergotamine ⁴ erlotinib estrogens etoposide everolimus ⁵ fentanyl ⁴ gefitinib haloperidol ibrutinib ⁵ idelalisib imatinib indinavir ⁵ irinotecan isavuconazole ⁵ itraconazole	atazanavir boceprevir clarithromycin cobicistat darunavir delavirdine grapefruit ³ grapefruit juice ³ idelalisib indinavir itraconazole ketoconazole lopinavir/ritonavir nefazodone nelfinavir posaconazole ritonavir saquinavir telaprevir telithromycin voriconazole	aprepitant conivaptan crizotinib diltiazem dronedarone erythromycin fluconazole fosamprenavir grapefruit ³ grapefruit juice ³ imatinib isavuconazole mifepristone nilotinib verapamil	barbiturates carbamazepine enzalutamide fosphenytoin phenobarbital phenytoin primidone rifampin St. John's wort	bosentan dabrafenib efavirenz etravirine modafinil naftillin rifapentine

ivacaftor				
ketoconazole				
lansoprazole				
lapatinib				
losartan				
lovastatin ⁵				
lurasidone ⁵				
macrolide antibiotics				
maraviroc ⁵				
medroxyprogesterone				
methadone				
midazolam ⁵				
midostaurin ⁵				
modafinil				
nefazodone				
nilotinib				
olaparib				
ondansetron				
osimertinib				
paclitaxel				
palbociclib				
pazopanib				
quetiapine ⁵				
quinidine ⁴				
regorafenib				
romidepsin				
saquinavir ⁵				
sildenafil ⁵				
simvastatin ⁵				
sirolimus ^{4,5}				
sonidegib				
sunitinib				
tacrolimus ^{4,5}				
tamoxifen				
telaprevir				
temsirolimus				
teniposide				
tetracycline				
tipranavir ⁵				
tolvaptan ⁵				
triazolam ⁵				
trimethoprim				
vardenafil ⁵				
vemurafenib				
venetoclax ⁵				
vinca alkaloids				
zolpidem				

¹ Certain fruits, fruit juices and herbal supplements (star fruit, Seville oranges, pomegranate, gingko, goldenseal) may inhibit CYP 3A4 isozyme, however, the degree of that inhibition is unknown.

² Refer to [Section 7.4.1](#) regarding use of corticosteroids.

³ The effect of grapefruit juice (strong vs moderate CYP3A4 inhibition) varies widely among brands and is concentration-, dose-, and preparation-dependent.

⁴ Narrow therapeutic range substrates

⁵ Sensitive substrates (drugs that demonstrate an increase in AUC of ≥ 5 -fold with strong inhibitors)

APPENDIX X: PATIENT DRUG INTERACTIONS HANDOUT AND WALLET CARD**Information for Patients, Their Caregivers and Non-Study Healthcare Team on Possible Interactions with Other Drugs and Herbal Supplements**

Patient Name:	Diagnosis:	Trial #:
Study Doctor:	Study Doctor Phone #:	Study Drug(s): MLN4924 (Pevonedistat)

Please show this paper to all your healthcare providers (doctors, physician assistants, nurse practitioners, pharmacists), and tell them you are taking part in a clinical trial sponsored by the National Cancer Institute.

These are the things that your healthcare providers need to know:

MLN4924 (pevonedistat) interacts with certain specific enzyme in your liver or other tissue like the gut and certain transport proteins that help move drugs in and out of cell.

CYP
isoenzymes

Explanation

The enzymes in question are CYP3A4/5. MLN4924 (pevonedistat) is broken down by CYP3A4/5 and may be affected by drugs that are moderate or strong inducers of CYP3A4/5. Use of CYP3A4 inducers (e.g., St. John's Wort, rifampin, phenytoin) is not allowed while taking MLN4924.

Transport
proteins

The transporter enzymes and proteins in question are P-glycoprotein (P-gp), OATP and BCRP. MLN4924 is moved in and out of cells/organs by P-gp and BCRP. Use caution with concomitant drugs that are inhibitors of P-gp. Concurrent use of drugs that are BCRP inhibitors (e.g., cyclosporine) is not allowed. MLN4924 may affect the ability of other drugs to be moved in and out of cells by inhibiting P-gp, OATP and BCRP. Use substrates of these transport proteins with caution.

These are the things that you need to know:

The study drug MLN4924 (pevonedistat), may interact with other drugs which can cause side effects. For this reason, it is very important to tell your doctors about all your medicines, including: (a) medicines you are taking before this clinical trial, (b) medicines you start or stop taking during this study, (c) medicines you buy without a prescription (over-the-counter remedy), (d) herbals or supplements (e.g. St. John's Wort). It is helpful to bring your medication bottles or an updated medication list with you.

Before you enroll onto the clinical trial, your study doctor will work with your regular health care providers to review any medicines and herbal supplements that are considered moderate or strong inhibitors or inducers of CYP3A4/5, P-gp, OATP and BCRP.

- Please be very careful! Over-the-counter drugs (including herbal supplements) may contain ingredients that could interact with your study drug. Speak to your doctors or pharmacist to determine if there could be any side effects. Avoid ingesting grapefruit and grapefruit juice.
- Make sure your doctor knows to avoid certain prescription medications.
- Your regular health care provider should check a frequently updated medical reference or call your study doctor before prescribing any new medicine or discontinuing any medicine.

Version JAN/2019

PATIENT DRUG INTERACTION WALLET CARD

NIH NATIONAL CANCER INSTITUTE EMERGENCY INFORMATION	NIH NATIONAL CANCER INSTITUTE	NIH NATIONAL CANCER INSTITUTE	NIH NATIONAL CANCER INSTITUTE DRUG INTERACTIONS
Show this card to all of your healthcare providers. Keep it with you in case you go to the emergency room.	Tell your doctors before you start or stop any medicines. Check with your doctor or pharmacist if you need to use an over-the-counter medicine or herbal supplement!		Carry this card with you at all times MLN4924 (pevonedistat) interacts with enzymes in your liver or other tissue like the gut, transport proteins that help move drugs in and out of cells and must be used very carefully with other medicines.
Patient Name: Diagnosis: Study Doctor: Study Doctor Phone #: NCI Trial #: Study Drug(S): MLN4924 (pevonedistat)	Use caution and avoid the following drugs if possible: St. John's Wort, grapefruit or grapefruit juice		Your healthcare providers should be aware of any medicines that are strong inhibitors/inducers of CYP3A4/5, P-gp and OATP. Drugs that are CYP3A4/5 inducers (e.g., rifampin, St. John's Wort), or BCRP inhibitors (e.g., cyclosporine) are not allowed. Before prescribing new medicines , your health care provider should check a frequently-updated medical reference for a list of drugs to avoid or contact your study doctor.
For more information: [name] cancer.gov clinicaltrials.gov	For more information: [name] cancer.gov clinicaltrials.gov	For more information: [name] cancer.gov clinicaltrials.gov	For more information: [name] cancer.gov clinicaltrials.gov

Version JAN/2019

THIS PROTOCOL IS FOR RESEARCH PURPOSES ONLY, SEE PAGE 1 FOR USAGE POLICY

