4.2.2 Concomitant Medications

4.2.2.1 Investigational Drugs: Patients who are currently receiving another investigational drug are not eligible.

4.2.2.2 Anti-cancer Agents: Patients who are currently receiving other anti-cancer agents are not eligible [except hydroxyurea, which may be continued until 24 hours prior to start of protocol therapy].

4.2.2.3 Anti-GVHD agents post-transplant:

Patients who are receiving cyclosporine, tacrolimus or other systemic agents to prevent graft-versus-host disease post bone marrow transplant are not eligible for this trial. Topical immunosuppressive agents (e.g. topical steroids) are allowed. Physiologic replacement of hydrocortisone is allowed.

4.2.2.4 Patients who are taking drugs that are strong CYP3A4 inducers and cannot be switched to alternative drugs 14 days prior to enrollment are not eligible. Strong inducers of CYP3A4 are not permitted during the study. See [Appendix IX](#) for more details.

4.2.3 Patients with known hepatitis B surface antigen seropositive or known or suspected active hepatitis C infection are not eligible. **NOTE:** Patients who have isolated positive hepatitis B core antibody (i.e. in the setting of negative hepatitis B surface antigen and negative hepatitis B surface antibody) must have an undetectable hepatitis B viral load. Patients who have positive hepatitis C antibody may be included if they have an undetectable hepatitis C viral load.

4.2.4 Patients with known hepatic cirrhosis or severe pre-existing hepatic impairment are not eligible.

4.2.5 Patients with uncontrolled high blood pressure (i.e., $\geq 99\%$ for age, see [Appendix XI](#)) are not eligible.

4.2.6 Patients with any of the following diagnoses:

- Acute promyelocytic leukemia
- Down syndrome
- Juvenile myelomonocytic leukemia

4.2.7 Infection: Patients who have a documented active uncontrolled infection are not eligible.

4.2.8 History of allergic reactions attributed to compounds of similar chemical or biologic composition as the study agent.

THIS PROTOCOL IS FOR RESEARCH PURPOSES ONLY, SEE PAGE 1 FOR USAGE POLICY

4.2.9 Patients with HIV are not eligible unless they meet all of the following criteria:

- CD4 count > 350 cell/mm³
- Undetectable viral load
- Maintained on modern therapeutic regimens utilizing non-CYP-interactive agents
- No history of AIDS-defining opportunistic infections

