6.2 Dose Modifications for Non-Hematological Toxicity

6.2.1 Patients will have ALT/AST/bilirubin evaluated prior to each planned dose of MLN4924 (pevonedistat) in order to determine whether the scheduled dose

should be administered. It is anticipated that ALT and AST may be elevated for approximately 48 hours following the end of the 1st MLN4924 (pevonedistat) infusion.

NOTE: See [Appendix III](#) for toxicity grading table.

If a patient experiences > Grade 3 elevation of ALT/AST on or after Cycle 1, Day 1 then the Cycle 1, Day 3 MLN4924 (pevonedistat) dose should not be given. If ALT/AST returns to \leq Grade 1 or baseline values by Day 5 then the patient should receive their Day 5 MLN4924 (pevonedistat) dose and this will not be considered a DLT. If ALT/AST does not return to \leq Grade 1 or baseline values by Day 5 then MLN4924 (pevonedistat) should be held and this will be considered a DLT. Persistent elevations of ALT/AST > Grade 2 beyond 2 days between any other doses after Cycle 1, Day 1 will be considered a DLT.

6.2.2 Patients who experience a dose limiting toxicity during cycle 1 that resolves to baseline or < Grade 1 at the time of next cycle can proceed with the next cycle at dose level -1.

6.3 **Modifications and Supportive Care Recommendations for Toxicity Related to Protocol Therapy (Cycle 1 and Cycle 2)**

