7.4.2 CYP3A4 Inducers and Inhibitors

In vitro, MLN4924 (pevoneditat) is metabolized predominantly by CYP3A4 with a small contribution from CYP2D6. Based on drug-drug interaction study results, administration of MLN4924 (pevoneditat) with moderate and strong CYP3A inhibitors and P-gp inhibitors is permitted, while use of strong CYP3A inducers should be avoided. Strong inducers of CYP3A4 should be discontinued within 14 days prior to the first dose of MLN4924 (pevoneditat) and are prohibited for the duration of the study (see [Appendix IX](#)).

7.4.3 Concomitant administration of BCRP inhibitors (e.g., cyclosporine, eltrombopag) should be avoided, however, limited use is permitted if clinically necessary and no suitable alternative exists. In this case, a patient may receive the BCRP inhibitor from 24 hours after the last MLN4924 (pevoneditat) dose until 72 hours before the next MLN4924 (pevoneditat) dose.

7.4.4 Acetaminophen and acetaminophen-containing products may be used judiciously but should not exceed a dose of 37 mg/kg/day (maximum 2 g in 24 hours) on days MLN4924 (pevoneditat) is administered.

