9.1.8 Potential drug interactions

Acetaminophen may be used judiciously but should not exceed a dose of 37 mg/kg/day (maximum 2 g in 24 hours) on days MLN4924 (pevonodistat) is administered.

In vitro, MLN4924 (pevonodistat) is metabolized via hydroxylation and oxidation, predominantly by CYP3A4 with a small contribution from CYP2D6 (approximately 3%). Based on drug-drug interaction study results, the administration of MLN4924 (pevonodistat) with moderate and strong CYP3A inhibitors and P-gp inhibitors is permitted, while the **use of strong CYP3A**

inducers should be avoided.

In vitro, MLN4924 (pevonedistat) does not inhibit the activities of CYP1A2, 2C9, 2C19, 2D6, and 3A4/5, but weakly and reversibly inhibits both CYP2B6 and 2C8; it does not induce CYP1A2, 2B6, and 3A4/5. Thus, MLN4924 (pevonedistat) is unlikely to affect the PK of drugs that are metabolized by these CYP450 isoforms.

MLN4924 (pevonedistat) is also a substrate for the drug efflux transporters, P-gp and BCRP, and a weak inhibitor of P-gp and BCRP-mediated transport. Additional in vitro transport studies showed that MLN4924 (pevonedistat) is not a substrate of the hepatic OATP, but it can inhibit OATP-mediated uptake of E3S and simvastatin and lovastatin. On the basis of these data and the recommended clinical dose range, MLN4924 (pevonedistat) is unlikely to affect the PK of other drugs that are known P-gp, BCRP, or OATP substrates, while the potential exists, albeit low, for drug interactions with BCRP inhibitors. Exclusion of P-gp inhibitors is not deemed warranted in clinical studies of MLN4924 (pevonedistat). However, the concomitant administration of BCRP inhibitors (e.g., cyclosporine, eltrombopag) should be avoided, however, limited use is permitted if clinically necessary and no suitable alternative exists. In this case, a patient may receive the BCRP inhibitor from 24 hours after the last MLN4924 (pevonedistat) dose until 72 hours before the next MLN4924 (pevonedistat) dose.

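### One panel of the Appendix X wallet card softens the ban on St. John's Wort, and neither the card nor the handout names the acetaminophen cap

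*Combined protocol and SAP*

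**What the plan says.** Appendix X holds a handout for patients, caregivers and health staff outside the study, and a wallet card that condenses it. One panel of the card reads: "Use caution and avoid the following drugs if possible: St. John's Wort, grapefruit or grapefruit juice".

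The rest of the plan is firmer. Section 4.2.2.4 states: "Strong inducers of CYP3A4 are not permitted during the study". Section 7.4.2 says that strong inducers "are prohibited for the duration of the study". The strong-inducer column of Appendix IX ends with "rifampin St. John's wort". The handout, and the drug-interactions panel of the same card, name St. John's Wort as an example of what is not allowed.

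On acetaminophen, Section 7.4.4 allows judicious use but says that it "should not exceed a dose of 37 mg/kg/day (maximum 2 g in 24 hours"), with the limit applying on days when pevonedistat is given. Section 9.1.8 repeats this among the potential drug interactions: "Acetaminophen may be used judiciously but should not exceed a dose of 37 mg/kg/day". The handout warns: "Over-the-counter drugs (including herbal supplements) may contain ingredients that could interact with your study drug". The card tells patients to ask a doctor or pharmacist before using such products. Neither names acetaminophen.

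**The concern.** The card is what a family carries and shows to others. On St. John's Wort it gives two different instructions, one of them weaker than the protocol. Section 2.2.3 describes pevonedistat as metabolized mainly by CYP3A4 and identifies inducers as the CYP3A4 interaction risk. A patient who took the weaker instruction at its word could therefore clear the drug faster. That would lower exposure and enter the pharmacokinetic summaries, which serve primary aim 1.1.3.

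On acetaminophen the issue is an omission. The protocol sets a numerical limit for a drug that families can buy without asking anyone. The patient material on drug interactions does not carry it, although the liver is the organ under watch: Section 6.2.1 anticipates that "ALT and AST may be elevated for approximately 48 hours" after the first infusion.

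**Working it through.** This is mainly a comparison of texts. The plan states no figure that needs reproducing.

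**1. St. John's Wort, place by place**

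| Place | Instruction |
|---|---|
| Section 4.2.2.4 | Strong inducers not permitted |
| Section 7.4.2 | Strong inducers to be avoided, then stated as prohibited throughout |
| Appendix IX | St. John's wort listed as strong |
| Appendix X, handout | Not allowed |
| Appendix X, card, drug-interactions panel | Not allowed |
| Appendix X, card, other panel | Avoid if possible |

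Only the last row allows any use. That panel groups St. John's Wort with grapefruit, which Appendix IX lists as a CYP3A4 inhibitor. Section 7.4.2 permits moderate and strong inhibitors, so the mild wording does no harm for grapefruit. It is wrong only for the inducer.

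**2. What could reach the pharmacokinetic data**

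Sampling is in Cycle 1 only (Section 8.2.2). It runs from before the Day 1 dose to at most 72 hours after the Day 5 infusion, that is, to about Day 5 + 3 = Day 8. Use after that cannot affect the measurements. Section 11.3 plans up to six evaluable patients per dose level, and Section 11.5 plans simple summary statistics. One affected patient would be 1/6 = 16.7% of a full cohort of six, or 1/12 = 8.3% if six expansion patients were pooled with it. The documents do not give the size of the fall in exposure or how often it would happen.

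**3. The acetaminophen cap in milligrams**

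Daily limit = the smaller of 37 × weight in kg and 2000 mg.

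- 10 kg: 37 × 10 = 370 mg
- 20 kg: 37 × 20 = 740 mg
- The 2 g ceiling applies from 2000 / 37 = 54.05 kg

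The cap covers Days 1, 3 and 5: three days per cycle, six over two cycles. Only the three in Cycle 1 fall in the DLT observation period (Section 5.6). A family cannot work out any of these amounts from the card.

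**4. Is use on those days foreseeable?**

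Yes. Fever is in the over-20% column for pevonedistat (Section 9.1.10) and for azacitidine (Section 9.2.2). Fever and headache are common within one to two days of intrathecal cytarabine (Section 9.3.2), which may be given as late as 24 hours before Day 1 (Section 5.2).

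**5. Is the liver a plausible concern?**

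Yes. In the adult azacitidine combination (Section 2.3.1), all four patients with a DLT had raised bilirubin (one) or raised AST and ALT (three). Two of the four were among the 55 treated at 20 mg/m²: 2/55 = 3.6%.

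**The case against.** The strongest reply is that patients are well protected without the change.

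- **Contact with staff.** The cap applies only on days when the patient comes for azacitidine and then a one-hour pevonedistat infusion. Liver tests must be read before every pevonedistat dose. On Days 1 and 5, pharmacokinetic sampling continues for 6–8 hours after the infusion (4–6 hours at 10 kg or less). Staff who work under Section 7.4.4 are present for part of every capped day. This stands, and it lowers the risk. It does not cover the hours at home.
- **Existing advice.** The card asks patients to tell their doctors before starting any medicine and has a field for the study doctor's telephone number. The handout and card also direct providers to a medical reference or the study doctor. This largely stands. The gap is that a pharmacist or general reference cannot be expected to know a study-specific cap.
- **The inducer ban appears elsewhere.** The handout and another panel state it correctly, and the handout says that the study doctor will review medicines and herbal products before enrollment. This narrows the fault to one panel, but that panel still contradicts the others.

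A reader might go further and infer that a missed cap would use up the single DLT that Section 11.3 allows among six patients, and so reduce the chance of confirming Dose Level 1. The documents do not support that. The inference takes an avoidable DLT as certain, while its frequency is unknown. Section 5.6.1.1 exempts Grade 3 or 4 ALT/AST rises that return to Grade 1 or less within 14 days. Section 6.2.1 does not count a rise above Grade 3 after Day 1 that has recovered by Day 5. Section 6.3.5 is stricter, but a transient rise is not simply a DLT. In adults at 20 mg/m² the transaminase rises were transient and resolved on their own.

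A reader might also infer from the dates (January 2019 on the handout and card, 08/15/20 on Section 9.1) that Appendix X was left out of date. The dates do not show when the cap was introduced.

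**Conclusion.** Both facts hold on the text. One panel gives patients an instruction that is wrong as written, and it bears on a primary aim. The acetaminophen omission is a gap rather than a contradiction, because nothing in the protocol requires Appendix X to carry the cap.

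The size is minor: a patient-safety consistency correction. It changes no sample size, DLT rule or analysis. The reduced exposure is an inference from Section 2.2.3, and the documents do not quantify it. The consent form was not in the text available for review and may state the cap, so it cannot be said that families are told nowhere.

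**What to change.** At the next amendment:

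- Delete St. John's Wort from the panel with the mild wording, so that the card shows it only as not allowed. Grapefruit can stay where it is.
- Add to the handout and the card: *Acetaminophen, including combination products: call the study team before use; on pevonedistat days do not exceed 37 mg/kg in 24 hours, never more than 2 g. Your maximum: ____ mg.* Staff can fill in the blank from the weight that Section 5.1 already requires within 7 days before each cycle.

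The cost is a few lines of patient material, IRB review and reissued cards for the patients enrolled (23 anticipated, 38 at most). A printed dose limit carries a small risk that families treat fever at home and mask it during neutropenia. The instruction to call first guards against that.

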APPENDIX XI: NEW YORK HEART ASSOCIATION CLASSIFICATION OF CARDIAC DISEASE

The following table presents the New York Heart Association classification of cardiac disease.³³

Class	Functional Capacity	Objective Assessment
III	Patients with cardiac disease resulting in marked limitation of physical activity. They are comfortable at rest. Less than ordinary activity causes fatigue, palpitation, dyspnea, or anginal pain.	Objective evidence of moderately severe cardiovascular disease
IV	Patients with cardiac disease resulting in inability to carry on any physical activity without discomfort. Symptoms of heart failure or the anginal syndrome may be present even at rest. If any physical activity is undertaken, discomfort is increased.	Objective evidence of severe cardiovascular disease

APPENDIX XII: CTEP AND CTSU REGISTRATION PROCEDURES

Food and Drug Administration (FDA) regulations and National Cancer Institute (NCI) policy require all individuals contributing to NCI-sponsored trials to register and to renew their registration annually. To register, all individuals must obtain a Cancer Therapy Evaluation Program (CTEP) Identity and Access Management (IAM) account (<https://ctepcore.nci.nih.gov/iam>). In addition, persons with a registration type of Investigator (IVR), Non-Physician Investigator (NPIVR), or Associate Plus (AP) (i.e., clinical site staff requiring write access to OPEN, RAVE, or TRIAD or acting as a primary site contact) must complete their annual registration using CTEP's web-based Registration and Credential Repository (RCR) (<https://ctepcore.nci.nih.gov/rcr>). Documentation requirements per registration type are outlined in the table below.

Documentation Required	IVR	NPIVR	AP	A
FDA Form 1572	✓	✓		
Financial Disclosure Form	✓	✓	✓	
NCI Biosketch (education, training, employment, license, and certification)	✓	✓	✓	
HSP/GCP training	✓	✓	✓	
Agent Shipment Form (if applicable)	✓			
CV (optional)	✓	✓	✓	

An active CTEP-IAM user account and appropriate RCR registration is required to access all CTEP and CTSU (Cancer Trials Support Unit) websites and applications. In addition, IVRs and NPIVRs must list all clinical practice sites and IRBs covering their practice sites on the FDA Form 1572 in RCR to allow the following:

- Added to a site roster
- Assigned the treating, credit, consenting, or drug shipment (IVR only) tasks in OPEN
- Act as the site-protocol PI on the IRB approval
- Assigned the Clinical Investigator (CI) role on the Delegation of Tasks Log (DTL).

Additional information can be found on the CTEP website at <<https://ctep.cancer.gov/investigatorResources/default.htm>>. For questions, please contact the RCR **Help Desk** by email at <[contact]>.

CTSU Registration Procedures

This study is supported by the NCI Cancer Trials Support Unit (CTSU).

IRB Approval:

Each investigator or group of investigators at a clinical site must obtain IRB approval for this protocol and submit IRB approval and supporting documentation to the CTSU Regulatory Office before they can be approved to enroll patients. Assignment of site registration status in the CTSU Regulatory Support System (RSS) uses extensive data to make a determination of whether a site has fulfilled all regulatory criteria including but not limited to the following:

- An active Federal Wide Assurance (FWA) number
- An active roster affiliation with the Lead Network or a participating organization
- A valid IRB approval
- Compliance with all protocol specific requirements.

In addition, the site-protocol Principal Investigator (PI) must meet the following criteria:

- Active registration status
- The IRB number of the site IRB of record listed on their Form FDA 1572
- An active status on a participating roster at the registering site.

Sites participating on the NCI CIRB initiative that are approved by the CIRB for this study are not required to submit IRB approval documentation to the CTSU Regulatory Office. For sites using the CIRB, IRB approval information is received from the CIRB and applied to the RSS in an automated process. Signatory Institutions must submit a Study Specific Worksheet for Local Context (SSW) to the CIRB via IRBManager to indicate their intent to open the study locally. The CIRB's approval of the SSW is then communicated to the CTSU Regulatory Office. In order for the SSW approval to be processed, the Signatory Institution must inform the CTSU which CIRB-approved institutions aligned with the Signatory Institution are participating in the study.

Requirements For ADVL1712 Site Registration:

- IRB approval (For sites not participating via the NCI CIRB; local IRB documentation, an IRB-signed CTSU IRB Certification Form, Protocol of Human Subjects Assurance Identification/IRB Certification/Declaration of Exemption Form, or combination is accepted)
- For applicable studies with a radiation and/or imaging (RTI) component, the enrolling site must be aligned to a RTI provider. To manage provider associations access the Provider Association tab on the CTSU website at <https://www.ctsu.org/RSS/RTFProviderAssociation>, to add or remove associated providers. Sites must be linked to at least one IROC credentialed provider to participate on trials with an RT component. Enrolling sites are responsible for ensuring that the appropriate agreements are in place with their RTI provider, and that appropriate IRB approvals are in place.

Submitting Regulatory Documents:

Submit required forms and documents to the CTSU Regulatory Office, where they will be entered and tracked in the CTSU RSS.

Regulatory Submission Portal: www.ctsu.org (members' area) → Regulatory Tab → Regulatory

THIS PROTOCOL IS FOR RESEARCH PURPOSES ONLY, SEE PAGE 1 FOR USAGE POLICY

Submission

When applicable, original documents should be mailed to:

CTSU Regulatory Office
[name]
[name]

Institutions with patients waiting that are unable to use the Portal should alert the CTSU Regulatory Office immediately at [name] in order to receive further instruction and support.

